#### Table 3b. Dose modifications (other)

\*The following actions should be taken only if toxicity may be possibly attributed to belantamab mafodotin.

	Severity	Management	Follow-up
	Grade 1	
 
Administer symptomatic treatment as appropriate.
 
Continue study drug(s).
 
	Provide close follow-up to evaluate for increased severity, no dose modification necessary
Events Not Otherwise Specified	Grade 2	
 
Administer symptomatic treatment.
 
Investigate etiology.
 
Consider consulting subspecialist, and/or diagnostic procedure.
 
	
 
Symptoms resolved in ≤7 days:
 
Continue after resolution at the current dose
 
Symptoms ongoing >7 days or worsening:
 
Consult study PI (cc: MCW Multisite Team email)
 
Delay study drug, or consider one dose level reduction. If recovery takes >3 weeks, consult with study PI (cc: MCW Multisite Team email)
 
If symptoms continue or worsen to grade 3–4, see below.
 

	Grade 3	
 
Provide appropriate medical treatment.
 
Consider consulting subspecialist.
 
	
 
Consult study PI (cc: MCW Multisite Team email).
 
Delay treatment till recovery to grade ≤ 1.
 
Consider dose reduction.
 
 Exceptions: Participants who develop grade 3

<sup>b If symptoms resolve within one hour of stopping infusion, the infusion may be restarted at 50% of the original infusion rate (e.g., from 100 mL/hr to 50 mL/hr). Otherwise, dosing will be held until symptoms resolve and the participant should be premedicated for the next scheduled dose.

		toxicities which respond to standard treatment and resolve to grade ≤ 1 within 48 hours may continue treatment at scheduled or reduced dose.
Grade 4	
 
Provide appropriate medical treatment.
 
Consider consulting subspecialist.
 
	Interrupt treatment.     Further treatment with belantamab mafodotin only allowed on individual basis if it is agreed between the site investigator and overall study PI (via email, cc: MCW Multisite Team email) that benefits outweigh the risks for a given participant

#### **5.2.3 Dose Modification Related Corneal Adverse Reactions**

All belantamab mafodotin dose modifications and stopping criteria are to be based on the Keratopathy Visual Acuity (KVA) Scale for Treatment-related Corneal Toxicities. Corneal events will be graded according to this scale. Refer to reporting section for additional requirements.

Table 4. Corneal adverse reactions and recommendations for belamantab mafodotin dosing.

Grade per KVA scale	Grade 1	Grade 2	Grade 3	Grade 4
*Recommended Dosage Modifications	Continue treatment at current dose.	Withhold belantamab mafodotin until improvement in both corneal examination findings and changes in BCVA to grade 1 or better and resume at current dose.	Withhold belantamab mafodotin until improvement in both corneal examination findings and changes in BCVA to grade 1 or better and resume at reduced dose.  If already on lowest dose, participant continues treatment at same dose.	Consider permanent discontinuation of belantamab mafodotin.  If based on benefit risk assessment and treatment of belantamab mafodotin is being considered, withhold treatment until improvement in both corneal examination findings and change in BCVA to grade 1 or better and resume at reduced dose.  If already on lowest dose, participant continues treatment at same dose.

Table 5: Keratopathy Visual Acuity (KVA) Scale for treatment-related corneal toxicities

Grade per KV	VA scale	Grade 1	Grade 2	Grade 3	Grade 4
	Corneal examination finding(s)	Mild superficial keratopathy a	Moderate superficial keratopathy b	Severe superficial keratopathy c	Corneal epithelial defect d
Corneal Toxicities	Change in BCVA e	Decline from baseline of one line on Snellen Visual Acuity	Decline from baseline of two or three lines (and Snellen Visual Acuity not worse than 20/200)	Decline from baseline by more than three lines (and Snellen Visual Acuity not worse than 20/200)	Snellen Visual Acuity worse than 20/200

Abbreviations: BCVA=Best-Corrected Visual Acuity; KVA=Keratopathy Visual Acuity.

Dose reductions of belantamab mafodotin will be triggered by grade 2 or worse events of ocular exam findings, or decrease in BCVA on day of dosing.

- a) Mild superficial keratopathy is mild superficial punctate keratopathy (documented worsening from baseline), with or without symptoms.
- b) Moderate superficial keratopathy is any/or a combination of moderate superficial punctate keratopathy, patchy microcyst like deposits, subepithelial haze (peripheral), or a new peripheral stromal opacity.
- c) Severe superficial keratopathy is any/or a combination of severe superficial punctate keratopathy, diffuse microcyst like deposits involving the central cornea, subepithelial haze (central), or a new central stromal opacity.
- d) Corneal epithelial defect such as corneal ulcers: corneal ulcer by definition means an epithelial defect with underlying stromal infiltration.
- e) Changes in visual acuity due to treatment-related corneal findings:
  - For participants who have BCVA worse than 20/20 in either eye at baseline, dose modification for that eye will be determined by the worsening of vision from baseline only (not by absolute BCVA at the visits).
  - If a participant has a baseline BCVA of 20/200 or worse in an eye, then belantamab mafodotin-related changes in vision in the other eye will drive the dose modification. If a participant has baseline BCVA of 20/200 or worse in both the eyes, then the decision to delay or reduce belantamab mafodotin dose will be based on site principal investigator's assessment of benefit vs. risk based on corneal examination findings following a discussion with the qualified eye care specialist.

Note: Dose modification should be based on the most severe finding. If eyes differ in severity, dose modification guideline should be applied based on the more severe eye.

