#### **5.2.2 Dose Reductions for Toxicity**

Permitted dose reductions for belantamab mafodotin are shown in **Table 2**. Belantamab mafodotin-related AEs are summarized in **Table 3**. General dose modification and management guidelines for drug-related AEs not otherwise specified are summarized in **Table 3**. Dose modification guidelines for cornea-related AEs associated with belantamab mafodotin are summarized in **Table 4**.

Table 2. Permitted dose reduction for belantamab mafodotin

Starting dose	First reduction	Additional reduction
1.9 mg/kg	1.4 mg/kg	If dose delays/modifications detailed below do not satisfy the conditions needed to avoid another dose reduction, the subject must be discontinued. Recommend emailing study PI (cc: MCW Multisite Team) prior to this occurring whenever possible.

Only one dose reduction (to 1.4 mg/kg) is permitted from the starting dose of 1.9 mg/kg. If the participant cannot tolerate the drug after the allowed dose reduction of belantamab mafodotin, the participant will permanently discontinue treatment for lack of tolerability. Any dose level below 1.4 mg/kg is not planned. In case of full resolution of symptoms which lead to dose reduction, further treatment at the previous dose level may be considered by the investigator, after consultation with the sponsor-investigator (cc: MCW Multisite Team email).

Dosing delays are permitted in the case of toxicity, medical/surgical events, or for logistical reasons not related to study therapy (e.g., elective surgery, unrelated medical events, subject's vacation/holidays, but not for subject's decision to delay treatment). The reason for any dose delay should be documented in the subject's eCRF and clinic record.

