Pneumonitis	Grade 2	
 
Withhold treatment with belantamab mafodotin.
 
Upon recovery, restart treatment with one dose-level reduction.
 
If patient is already at the lowest dose level (1.4 mg/kg), then rechallenge with the same dose; this must be discussed with the study PI.
 
	
	Grades 3–4	Permanently discontinue treatment with belantamab mafodotin.	
Urine dipstick	2+	
 
May continue belantamab mafodotin dosing.
 
Confirm by quantitative assessment using albumin/creatinine (spot urine from first void).
 
If albumin/creatinine ≥2,000 mg/g, at the next cycle follow guidance above for spot urine.
 
	
	≥3+	Interrupt treatment and follow up for recovery.  Implement quantification of albumin/creatinine ratio.	

<sup>a These criteria do not apply to participants on dialysis.

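### Section 5.2.3 gives two different doses after a KVA grade 2 corneal event: Table 4 resumes at the current dose, the note under Table 5 reduces it

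*Combined protocol and SAP*

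**What the plan says.** Section 5.2.3 opens by putting all corneal dosing decisions on one scale: "All belantamab mafodotin dose modifications and stopping criteria are to be based on the Keratopathy Visual Acuity (KVA) Scale". Table 4 then gives the action for each KVA grade.

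- Grade 1: treatment continues at the current dose.
- Grade 2: treatment is held until recovery in both components, in the words "changes in BCVA to grade 1 or better and resume at current dose".
- Grade 3: the same hold, but "changes in BCVA to grade 1 or better and resume at reduced dose".
- Grade 4: permanent discontinuation is considered. If treatment goes on, the hold and the reduced dose apply as at grade 3.

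The grade 3 and grade 4 cells add that a participant already at the lowest dose stays on that dose. The grade 2 cell has no such line.

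The note under Table 5, in the same section, reads "Dose reductions of belantamab mafodotin will be triggered by grade 2 or worse events of ocular exam findings, or decrease in BCVA", and ends by tying this to the day of dosing.

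Section 5.2.2 supplies the dose levels: "Only one dose reduction (to 1.4 mg/kg) is permitted from the starting dose of 1.9 mg/kg". It also directs the reader to Table 4: "Dose modification guidelines for cornea-related AEs associated with belantamab mafodotin are summarized in" that table.

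**The concern.** Both rules apply to a grade 2 finding at the pre-dose eye examination, and they give different next doses. The note is worded as a definite instruction, whereas the action row of Table 4 is headed as a recommendation. A site could follow either one in good faith and depart from the other.

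Two things are at stake. The first is consistent dosing: the same eye finding could lead to 1.9 mg/kg at one of the three anticipated sites and 1.4 mg/kg at another. The second is the reduction step itself. Only one is allowed, so a site that follows the note spends it on an event for which Table 4 would keep the dose. Table 2 requires discontinuation if a further reduction cannot be avoided.

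Corneal events are on the protocol's list of adverse events of special interest. Section 1.4 reports keratopathy as the most common reason for dose reduction in the cited single-agent study. That study used 2.5 mg/kg every three weeks, so its rate is not carried over to 1.9 mg/kg every eight weeks.

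**Working it through.** The check is mainly a comparison of texts; no sample size, power or event figure is involved.

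**Step 1. Is it the same scale and the same event?** Section 5.2.3 bases every corneal modification on the KVA scale, so the grade in the note is a KVA grade. The note's visual-acuity trigger is read the same way, as a decline of grade 2 or worse. On that reading there is no conflict at grade 1.

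**Step 2. Does the day-of-dosing qualifier separate the two rules?** No. Section 5.2.4 requires an eye examination before every dose, at most five days ahead and as close to dosing as possible. A grade 2 finding at that examination, still present on the dosing day, falls under both rules.

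**Step 3. Does reduction mean a lower dose?** In this protocol it ordinarily does.

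- Footnote e of Table 5 names delay and reduction as alternatives: "the decision to delay or reduce belantamab mafodotin dose will be based on" the site investigator's assessment.
- The grade 2 pneumonitis row of Table 3a first holds the drug and then says "Upon recovery, restart treatment with one dose-level reduction".
- Section 5.2.2 uses the word for the step from 1.9 to 1.4 mg/kg.

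**Step 4. Compare the rules by grade, for a participant on 1.9 mg/kg.**

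| KVA grade | Table 4 | Note under Table 5 | Agree? |
|---|---|---|---|
| 1 | continue 1.9 | not triggered | yes |
| 2 | hold, resume 1.9 | reduce to 1.4 | **no** |
| 3 | hold, resume 1.4 | reduce to 1.4 | yes |
| 4, if treatment continues | hold, resume 1.4 | reduce to 1.4 | yes |

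The conflict is in one grade of four.

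**Step 5. Size of the difference.** The inputs are the two dose levels (Section 5.2.2) and the example weight of 97.2 kg (Section 7.1.6).

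- Relative difference: (1.9 − 1.4) / 1.9 = 0.5 / 1.9 = 26.3%.
- Dose under Table 4: 97.2 × 1.9 = 184.68 mg, which matches the protocol's own worked example.
- Dose under the note: 97.2 × 1.4 = 136.08 mg.
- Difference: 184.68 − 136.08 = 48.60 mg.
- Reductions used: none under Table 4, one of the one permitted under the note.

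**Step 6. Is there a rule that settles it?** Section 5.2.2 points to Table 4 but does not say that it overrides the note. The closing note of Section 5.2.3, on the most severe finding and the worse eye, decides which grade applies, not what to do at that grade. Nothing else in Sections 5.2.2 to 5.2.4 reconciles the two.

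**The case against.** The strongest reply is that this is a one-word slip. Section 5.2.3 otherwise speaks of dose modification: in its title, its opening sentence, the Table 4 row label, footnote e and its closing note. Grade 2 is also where the first modification in Table 4, the hold, begins. If the note is read as modifications, it matches Table 4 at every grade. It sits under a grading scale and gives no dose level, hold or recovery threshold, so a site must go to Table 4 to act on it.

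The consequences are also limited. A later grade 3 corneal event at 1.4 mg/kg does not force discontinuation, because Table 4 keeps such a participant on the same dose; grade 2 pneumonitis allows rechallenge at 1.4 mg/kg. Section 5.2.2 lets the investigator consider returning to the previous dose after full resolution, in consultation with the sponsor-investigator. Section 5.2.4 has corneal findings managed in contact with the lead investigator. A misreading errs toward less drug, at a level the protocol itself defines.

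Most of this stands as a statement of probable intent and of limited effect. It does not remove the conflict. The sentence says reductions, the protocol elsewhere distinguishes reductions from holds, and precedence is left to inference. Return to the higher dose is discretionary. The spent step can still matter for other toxicities: in Table 3a, grade 3 thrombocytopenia without bleeding and restart after confirmed albuminuria both call for a one-level reduction, and neither row has the lowest-dose allowance.

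**Conclusion.** The concern holds: the note under Table 5 is wrong as written, or else the grade 2 cell of Table 4 is. The table is probably right, because Section 5.2.2 sends the reader there and because its lowest-dose line appears only in the cells where the dose is reduced.

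The size is one KVA grade of four, a next dose of 1.9 or 1.4 mg/kg (26% lower), and use of the single permitted reduction. This assumes a participant on the starting dose, a grade 2 finding present on the dosing day, and the ordinary meaning of reduction. The documents do not allow an estimate of how many participants would be affected. No effect is claimed on the primary endpoint, the grade 4 corneal monitoring boundary, power or type I error.

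It should be fixed because the sentence directs dosing and, followed literally, changes the dose given.

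**What to change.** Replace the note under Table 5 with wording such as:

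> A KVA grade of 2 or worse, by corneal examination or by change in best-corrected visual acuity from baseline, triggers a dose hold. A KVA grade of 3 or worse triggers a dose reduction on resumption. Table 4 governs.

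If the sponsor does intend reduction at grade 2, amend the grade 2 cell of Table 4 instead so that treatment resumes at the reduced dose, and state there what happens to a participant already at 1.4 mg/kg, as the grade 3 and 4 cells do.

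Either route is a wording correction and a notice to sites. Sample size, power and type I error are unchanged.

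### For a KVA grade 2 corneal event, Table 4 says hold and resume at the current dose, but the note under Table 5 says grade 2 triggers a dose reduction

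*Combined protocol and SAP*

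**What the plan says.** Section 5.2.3 opens by basing every belantamab mafodotin dose modification on the KVA scale, so a grade means the same thing throughout the section. Table 4 then sets the action by grade:

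- Grade 1: "Continue treatment at current dose".
- Grade 2: withhold until improvement in corneal findings and "changes in BCVA to grade 1 or better and resume at current dose".
- Grade 3: withhold until improvement in corneal findings and "changes in BCVA to grade 1 or better and resume at reduced dose".
- Grade 4: consider stopping permanently; if treatment is to go on, hold and resume at the reduced dose.
- Grades 3 and 4 at the lowest level: "If already on lowest dose, participant continues treatment at same dose".

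The note under Table 5, the grading table, reads: "Dose reductions of belantamab mafodotin will be triggered by grade 2 or worse events of ocular exam findings, or decrease in BCVA", with the qualifier that this applies on the day of dosing.

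Section 5.2.2 refers the reader to Table 4: "Dose modification guidelines for cornea-related AEs associated with belantamab mafodotin are summarized in" that table. It allows one reduction only, from 1.9 to 1.4 mg/kg, and deals with dose delays separately.

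**The concern.** At grade 2 the two instructions cannot both be followed. An investigator who reads Table 4 restarts at 1.9 mg/kg, and one who reads the note restarts at 1.4 mg/kg. A monitor could cite either as a deviation from the other.

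The situation is foreseeable. Section 1.4 reports keratopathy of any grade in 67 of 95 patients (71%) at 2.5 mg/kg every three weeks in DREAMM-2. Section 5.2.4 requires an eye examination before every dose.

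Two things are at stake. The first is the dose on resumption, and so the regimen that the efficacy and toxicity results describe. The second is the single permitted reduction. For corneal events its loss matters little, because Table 4 lets a patient at the lowest dose carry on. For other toxicities it can matter. Table 3a, for example, asks for a one-level reduction at grade 3 thrombocytopenia without bleeding, and a patient already at 1.4 mg/kg has no level left.

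**Working it through.** The plan has no figure of its own to reproduce here. The check sets the two instructions side by side and then sizes the one place where they differ.

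**Step 1. Compare by KVA grade, for a patient at 1.9 mg/kg examined before a dose.**

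| KVA grade | Table 4: dose on resumption | Note under Table 5 | Agree? |
|---|---|---|---|
| 1 | 1.9 mg/kg, no hold | no reduction (below grade 2) | yes |
| 2 | 1.9 mg/kg after a hold | reduction, so 1.4 mg/kg | **no** |
| 3 | 1.4 mg/kg after a hold | reduction, so 1.4 mg/kg | yes |
| 4, if resumed | 1.4 mg/kg after a hold | reduction, so 1.4 mg/kg | yes |

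The conflict is confined to grade 2.

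**Step 2. Look for text that reconciles the two.**

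- The timing qualifier does not. Section 5.2.4 places the eye examination within five days before dosing, so Table 4 is applied at the same decision point.
- Reading reduction loosely as any modification is not supported by the wording. Section 5.2.2 uses the word for the step to 1.4 mg/kg, and Table 4 sets the current dose against the reduced dose.
- Footnotes a to e and the closing note cover grade definitions, baseline acuity and which eye governs. None sets an order of precedence.
- Section 5.2.2 points to Table 4 but does not say that it overrides the note. Table 4's actions are headed as recommended, while the note is phrased as mandatory.

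**Step 3. Size the difference per dose.** The inputs are the two dose levels in Table 2.

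(1.9 − 1.4) / 1.9 = 0.5 / 1.9 = 0.263, or 26% lower.

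**Step 4. Count the reductions left after one grade 2 event.** One is permitted. Under Table 4, 1 − 0 = 1 remains. Under the note, 1 − 1 = 0 remains.

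**Step 5. Try to estimate how many patients would be affected.** This would need the rate of KVA grade 2 events at 1.9 mg/kg every eight weeks, which the documents do not give. The 71% is any-grade keratopathy on a higher and more frequent dose. The early BelaRd data in Section 1.3 cover 18 patients on a combination regimen, with one grade 2 punctate keratopathy, at 2.5 mg/kg. Neither gives a usable rate.

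**The case against.** The strongest reply is that Table 4 plainly governs. Section 5.2.2 names it as the corneal guideline, the note sits under a grading table, and Table 4 takes care to separate grade 2 from grade 3. In addition, only three sites are planned, and Section 5.2.4 requires corneal findings to be managed in close communication with the lead investigator, so unnoticed divergence between sites is less likely. Both texts lead to a dose the protocol permits, and Section 5.2.2 lets the earlier dose be restored after full resolution of symptoms and consultation.

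Much of this stands. Table 4 is probably the intended rule, and central contact lowers the risk. But probable intent is not a precedence rule, restoration is discretionary, and the note still tells a site to do something else.

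Three stronger readings are tempting, and the documents do not support them.

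- *Any fall in visual acuity triggers a reduction.* The acuity part of the note carries no grade of its own, and grade 1 in Table 5 is "Decline from baseline of one line on Snellen Visual Acuity". But the section bases all modifications on the KVA scale, which grades acuity as well as corneal findings. The natural reading is grade 2 or worse for both.
- *A grade 2 event at 1.4 mg/kg forces discontinuation.* Table 2 says: "If dose delays/modifications detailed below do not satisfy the conditions needed to avoid another dose reduction, the subject must be discontinued". Table 4 is among those later rules. It resumes grade 2 at the current dose and lets grades 3 and 4 go on at the lowest dose, so stopping for grade 2 alone is not credible.
- *The conflict costs a stated share of cumulative dose to month 12.* That depends on the length of the hold. Section 1.4 gives a median recovery of 86.5 days (range 8 to 358) on the three-weekly regimen. The 16-week point in note 9 of the study calendar says only that the patient may discontinue. No cumulative figure can be defended from these.

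**Conclusion.** The inconsistency is real and limited to KVA grade 2. As written, the note and the grade 2 cell of Table 4 cannot both be applied. The consequence for a patient at 1.9 mg/kg is a resumption dose of 1.9 or 1.4 mg/kg, a difference of 26% per dose, and the loss of the only permitted reduction if the note is followed.

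No effect on progression-free survival is shown. Sample size, power and alpha do not depend on this wording, and the formal corneal stopping rule in Section 8.2.5 counts grade 4 events only.

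The conclusion assumes that reduction has its Section 5.2.2 meaning. It also assumes that no lost text settles the matter: the action row of Table 4 carries an asterisk whose footnote is not visible in the text available. That Table 4 was intended is an inference for the sponsor to confirm. The point is worth correcting in the next amendment because it is a stated dosing rule for the drug's most common toxicity.

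**What to change.** Once the sponsor confirms that Table 4 is the intended rule, replace the note under Table 5 with:

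> Dose modifications of belantamab mafodotin will be triggered by KVA grade 2 or worse corneal examination findings or change in BCVA on day of dosing, as set out in Table 4 (grade 2: hold and resume at current dose; grade 3: hold and resume at reduced dose; grade 4: consider permanent discontinuation, otherwise hold and resume at reduced dose; if already at 1.4 mg/kg, resume at 1.4 mg/kg).

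If reduction at grade 2 was intended, keep the note and change the grade 2 cell of Table 4 to resumption at the reduced dose, with the same lowest-dose provision as grades 3 and 4.

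Either way the cost is one replaced passage in the next amendment and a memo to the sites. No new data, visits or patients are needed.
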